## 12.7. Appendix 7: Study Tabular Summary

Parameter Group	Parameter	Value
Trial information	Trial Title	A Randomized, Double-Blind, Placebo-Controlled, Study to Assess the Efficacy, Safety, Pharmacokinetics and Pharmacodynamics of AGN-242428 in Patients With Plaque Psoriasis
	Clinical Study sponsor	Vitae Pharmaceuticals Inc., an Allergan affiliate
	Trial Phase Classification	Phase 2b Trial
	Trial Indication	Plaque psoriasis
	Trial Indication Type	Treatment
	Trial Type	Efficacy Safety
	Trial Length	22 weeks $\pm$ 3 days from screening to follow-up
	Planned Country of Investigational Sites	United States
	Planned Number of Participants	200
	FDA-Regulated Device Study Indicator	No
Participant information	FDA-Regulated Drug Study Indicator	Yes
	Pediatric Study Indicator	No
	Diagnosis Group	Moderate to severe plaque psoriasis defined as PASI $\geq$ 12, % BSA $\geq$ 10 and PGA of $\geq$ 3
	Healthy Participant Indicator	No
	Planned Minimum Age of Participants	18
	Planned Maximum Age of Participants	75
	Sex of Participants	Male/Female
	Stable Disease Minimum Duration	6 months

AGN-242428

Parameter Group	Parameter	Value
Treatments	Investigational Therapy or Treatment	AGN-242428
	Intervention Type	Drug
	Pharmacological Class of Invest. Therapy	Selective, orally active small molecule inhibitor of ROR $\gamma$ t activity
	Dose per Administration	[REDACTED]
	Dose Units	[REDACTED] and [REDACTED] capsules
	Dosing Frequency	Once-daily
	Route of Administration	Oral
	Current Therapy or Treatment	Current treatment or history of treatment with immunosuppressive therapy, for any condition, within 4 weeks of study, unless otherwise stated is prohibited. Current treatment or history of treatment with any anti-TNF $\alpha$ biologic therapy within 3 months or 5 half-lives of study, and/or all other biologics within 6 months of study (Day 1) is prohibited. Current treatment or history of treatment for psoriasis with non-biologic systemic medications or UV therapy within 4 weeks of Day 1 and treatment with topical agents within 2 weeks of Day 1 is prohibited.
	Added on to Existing Treatments	No
	Control Type	Placebo
	Comparative Treatment Name	Not applicable
Trial design	Study Type	Interventional
	Intervention Model	Parallel
	Planned Number of Arms	4
	Trial is Randomized	Yes
	Randomization Quotient	1:1:1:1 ([REDACTED] AGN-242428: [REDACTED] AGN-242428: [REDACTED] AGN-242428: placebo).
	Trial Blinding Schema	Double blind
	Stratification Factor	No
	Adaptive Design	No
	Study Stop Rules	A participant will be permanently withdrawn from study treatment if any of the criteria below are met and considered related to AGN-242428:

AGN-242428

Parameter Group	Parameter	Value
		
Study Treatment-related SAE
 
Decreased total leukocyte count; Leukopenia < 3000/<math>\mu</math>L (< 3.0 x 10^9/L)
 
Decreased total neutrophil count; Neutropenia < 1000/<math>\mu</math>L (< 1.0 x 10^9/L)
 
Decreased total lymphocyte count; Lymphopenia < 500/<math>\mu</math>L (< 0.5 x 10^9/L)
 
Decreased platelet count; Thrombocytopenia < 100,000/<math>\mu</math>L (< 100 x 10^9/L)
 
Increased serum creatinine; Serum creatinine > 2 x ULN
 
Unspecified safety concern; Upon request by investigator or Medical Safety Physician
 
Increased liver enzymes:
 
 
•ALT and/or AST <math>\geq</math> 5 x ULN
 
•ALT and/or AST <math>\geq</math> 3 x ULN AND TBL <math>\geq</math> 2 x ULN or INR > 1.5
 
•ALT and/or AST <math>\geq</math> 3 x ULN with symptoms
 

AGN-242428

**12.8. Appendix 8: Partial List of Prohibited Medications Which Are Sensitive Substrates for BCRP, OATP1B3, CYP2D6, and CYP2C8 and Strong Inhibitors or Inducers of CYP3A4**

This list of prohibited medications is provided as a guidance. Use of these medications is prohibited unless approved by the investigator or sponsor. This list is not comprehensive and the investigators will consult with the sponsor before allowing concomitant medication use during the trial.

**Partial List of Prohibited Substrates**

BCRP Substrates	OATP1B3 Substrates	CYP2D6 Substrates	CYP2C8 Substrates	CYP3A4 Inhibitors	CYP3A4 Inducers
Apixaban	Atorvastatin	Amitriptyline	Amiodarone	Bitter Orange supplement	Carbamazepine
Methotrexate	Methotrexate	Aripiprazole	Pioglitazone	Clarithromycin	Guggul ( Commiphora mukul )
Rivaroxaban	Pravastatin	Atomoxetine	Repaglinide	Grapefruit	Phenobarbital
Rosuvastatin	Rifampin	Carvedilol		Grapefruit Juice	Phenytoin
Sulfasalazine	Rosuvastatin	Chlorpheniramine		Itraconazole	Primidone
		Desipramine		Ketoconazole	Rifampin
		Dextromethorphan		Resveratrol	St. John's Wort
		Doxepin		Seville oranges	
		Fluoxetine		Seville orange juice	
		Imipramine			
		Metoprolol			
		Mirtazapine			
		Nortriptyline			
		Paroxetine			
		Propafenone			
		Propranolol			
		Risperidone			
		Tolterodine			

Use of drugs or substances known to be sensitive cytochrome P450 CYP2D6 or CYP2C8 substrates, strong CYP3A4 inhibitors, strong CYP3A4 inducers, or transported by specific liver transporters (ie, breast cancer resistance protein [BCRP] and/or organic anion transporting polypeptide 1B3 [OATP1B3]) is prohibited unless approved by the investigator and sponsor.

AGN-242428

## 12.9. Appendix 9: Protocol Amendment History

The protocol amendment summary of changes table for the current amendment (Amendment 2) is located directly before the table of contents.

The rationale and the protocol amendment summary of changes table for Amendment 1 is located below:

### Overall Rationale for Amendment 1:

The overall rationale for the changes implemented in the protocol amendment was 1) to align the inclusion/exclusion criteria with industry precedence for similar psoriasis studies, 2) to add INR monitoring to the stopping criteria to adhere to FDA Guidance for DILI 2009, and 3) to add INR monitoring to the Adverse Events of Special Interest for additional safety surveillance.

Section No. and Name	Description of Change	Brief Rationale
6.1 Inclusion Criteria	Removed the following phrase from Inclusion Criterion 3.01: “and body mass index (BMI) within the range 18 to 35 kg/m  inclusive”	To align the inclusion/exclusion criteria with industry precedence for similar psoriasis studies
6.2 Exclusion Criteria	Removed the following statement from Exclusion Criterion 1.02: “Stable is defined as psoriasis that has not worsened or improved resulting in a 1% change in total body surface area (BSA) or a 2-point change in total Psoriasis Area and Severity Index (PASI) score.”	To align the inclusion/exclusion criteria with industry precedence for similar psoriasis studies
Table 7-1	Deleted “Manufactured for Allergan by Frontage Laboratories, Inc.”	In the event there is a change in the manufacturer
Table 8-1 Safety Criteria for Individual Participants Stopping Study Treatment	Added INR to stopping criteria here and throughout the protocol	Adhere to FDA Guidance for DILI 2009
9.1.1 Determination of Percent Body Surface Area	Added “(handprint method)”	Clarified the BSA methodology
9.1.2 Psoriasis Area and Severity Index	Added “(handprint method)” and text on the surface area involvement of each of the 4 anatomic regions and how they are scored.	Clarified the PASI methodology and aligned the PASI descriptors with industry precedents
Section 9.2.8 Adverse Events of Special Interest	Added INR to Adverse Events of Special Interest here and throughout the protocol	Additional safety surveillance
12.4 Contraceptive Guidance	Deleted footnote b from the table, which stated: “Hormonal contraception may be susceptible to interaction with the study treatment, which may	Deleted for clarity to match the text in the protocol, which states: “...agree to use 2 forms

AGN-242428

Section No. and Name	Description of Change	Brief Rationale
Throughout	reduce the efficacy of the contraceptive method. In this case, 2 highly effective methods of contraception should be utilized during the treatment period and for 30 days after the last dose of study treatment.” Minor editorial revisions	of birth control, in which at least 1 form must be a highly effective method of contraception.” Minor, therefore have not been summarized

3.0 LIST OF ABBREVIATIONS

AE	adverse event
AESI	adverse event of special interest
ANCOVA	analysis of covariance
BSA	Body Surface Area
CMH	Cochran-Mantel-Haenszel
CRF	case report form
ECG	electrocardiogram, electrocardiographic
ITT	modified intent to treat
MedDRA	Medical Dictionary for Regulatory Activities
PASI	Psoriasis Area and Severity Index
PGA	Physician's Global Assessment
PRO	Patient Reported Outcomes
PT	Preferred Term
QTc	QT interval corrected for heart rate
SAE	serious adverse event
SAP	statistical analysis plan
SOC	System Organ Class
TEAE	treatment-emergent adverse event

4.0 INTRODUCTION

This statistical analysis plan (SAP) provides a more technical and detailed elaboration of the statistical analyses of the efficacy and safety data as outlined and/or specified in the final protocol of Study 1957-201-001 (dated 29 Jun 2017) and the most recent amendment 2 (dated 21 Dec 2017). Specifications of tables, figures, and data listings are contained in a separate document. The SAP for pharmacokinetic/pharmacodynamic and health economics and outcomes research data will be prepared separately.

Study 1957-201-001 is a Phase 2b, double-blind, randomized, placebo-controlled trial to evaluate the efficacy, safety, tolerability, pharmacokinetics, and pharmacodynamics of AGN-242428 when administered once daily for 16 weeks to adults with moderate to severe plaque psoriasis.

Approximately 200 participants were planned to be randomly assigned (1:1:1:1) to once-daily study medication (50 participants to AGN-242428 225 mg, 50 participants to AGN-242428 350 mg, 50 participants to AGN-242428 450 mg and 50 participants to placebo) to provide an estimated total of 160 evaluable participants who will complete the study. The study consists of 3 periods, as described below.

Screening Period: The purpose of the Screening period is to evaluate potential study participants and to qualify them for enrollment into the study. This period begins at the point of informed consent and ends when the participant is randomized to treatment. The screening period will be up to 4 weeks (\leq 28 days) in duration.

Treatment Period: Participation in the study begins at the point the participant is randomized. The treatment starts after his/her first dose of study medication and ends after 16 weeks of treatment or at the point of permanent study medication withdrawal should the participant discontinue treatment prior to completion of Week 16.

[figure not shown]
On Day 1 of the treatment period, qualified participants will be randomly assigned to receive 16 weeks of once-daily oral treatment with [REDACTED] AGN-242428, [REDACTED] AGN-242428, [REDACTED] AGN-242428, or placebo. Baseline data for evaluation of participant efficacy and safety will be obtained on Day 1, prior to receiving the first dose. Participants will complete study visits on the first day of treatment and following 2, 4, 6, 8, 10, 12, and 16 weeks of treatment for evaluation of efficacy, safety, and tolerability assessments.

[figure not shown]
Any participant who exhibits a predefined change in clinical laboratory parameters may be required to complete unscheduled visits to further monitor abnormal safety laboratory test results. Investigators may complete unscheduled study visits at any point they feel necessary to

[figure not shown]
monitor and ensure participant safety. [REDACTED]
[REDACTED]
[REDACTED]
[REDACTED]
[REDACTED]

[figure not shown]
Follow-up Period: Participants will return for a follow-up visit 14 ± 3 days after completion of study medication or after early withdrawal for end-of-study assessments.

[figure not shown]
The schedule of evaluations for Study 1957-201-001 is presented in Table 4-1.

[figure not shown]

[figure not shown]

[figure not shown]

5.0 OBJECTIVES

The objectives of this study are:

- To compare the efficacy of AGN-242428 with placebo, with respect to Psoriasis Area and Severity Index (PASI) score and Physician's Global Assessment (PGA) score, in participants with moderate to severe plaque psoriasis
- To assess the safety and tolerability of AGN-242428 in participants with moderate to severe plaque psoriasis
- To characterize the pharmacokinetics of AGN-242428 in participants with moderate to severe plaque psoriasis

6.0 PATIENT POPULATIONS

The patient populations will be summarized in total and by treatment group for all randomized or treated participants.

6.1 MODIFIED INTENT-TO-TREAT POPULATION

The modified Intent-to-Treat (mITT) Population will consist of all randomized participants with at least 1 postbaseline PASI assessment.

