## 8. Discontinuation/Withdrawal Criteria

Withdrawn participants are those who do not complete all evaluations and procedures outlined in the protocol. Participants who discontinue taking study medication for any reason must also be withdrawn from the study. All AEs that are present when the participant withdraws from the study will be followed as described in Section 9.2.

Participants may voluntarily withdraw from the study at any time.

Notification of early participant discontinuation from the study and the reason for discontinuation will be made to the sponsor and will be clearly documented on the appropriate eCRF.

Reasons for discontinuation from the study treatment and/or the study may include the following:

- AE
- Death
- Lost to follow-up
- Non-compliance with study drug
- Meets study defined stopping criteria
- Investigator decision
- Pregnancy
- Protocol deviation
- Screen failure
- Site terminated by sponsor
- Study terminated by sponsor
- Withdrawal by subject
- Completed
- Other

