### 10.2. Populations for Analyses

The analysis populations will consist of participants as defined in [Table 10-1](#).

**Table 10-1** Analysis Populations

Population	Definition	Study Treatment
Modified intent-to-treat (mITT)	All randomized participants with at least 1 postbaseline PASI assessment. This population will be used for all efficacy analysis.	Randomized assignment
Pharmacokinetic (PK)	All participants who received AGN-242428 and had available plasma concentration data. The PK analysis set will be used for all PK analyses.	Actual received
Pharmacodynamic (PD)	All participants for whom PD measurements are available at baseline and at least one postbaseline visit.	Actual received
Safety	All participants who received $\geq 1$ administration of study treatment.	Actual received

PASI = Psoriasis Area and Severity Index

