10.0 EFFICACY ANALYSES

The efficacy analyses will be based on the mITT Population, defined as randomized participants with at least 1 postbaseline PASI assessment. *Baseline* for efficacy is defined as the last non-missing efficacy assessment before the first dose of study treatment. All efficacy analyses will be conducted using observed data. All statistical tests will be 2-sided hypothesis tests performed at the 5% level of significance for main effects. All confidence intervals will be 2-sided 95% confidence intervals, unless stated otherwise.

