10.1 PRIMARY EFFICACY PARAMETER

The primary efficacy endpoint will be percentage of participants achieving a reduction (improvement) in PASI score of $\geq 75\%$ from baseline to Week 16.

The null hypothesis is that the population responder rates of the AGN-242428 and placebo groups are the same. The alternative hypothesis is that the rates differ:

- $H_0: r_v = r_p$
- $H_a: r_v \neq r_p$

where r_v and r_p are the population rates in the AGN-242428 and placebo groups, respectively.

Frequency counts of participants achieving a $\geq 75\%$ reduction in PASI score relative to baseline will be tabulated by treatment at each postbaseline visit. The difference between each of the AGN-242428 groups and placebo in the proportion of participants with a reduction in PASI of $\geq 75\%$ from baseline, will be analyzed using a Chi-Square test.

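### The mITT rule makes efficacy analysis conditional on a PASI score after baseline; it should be changed together with the observed-data rule, because counting missing Week 16 scores as non-response inside mITT would still leave out anyone never scored

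*SAP*

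**What the plan says.** SAP 6.1 says that the mITT population "will consist of all randomized participants with at least 1 postbaseline PASI assessment". Protocol Table 10-1 gives the same definition and adds: "This population will be used for all efficacy analysis". SAP 10.0 repeats it: "The efficacy analyses will be based on the mITT Population, defined as randomized participants with at least 1 postbaseline PASI assessment". Neither document plans an efficacy analysis of all randomised or all dosed participants, even as a sensitivity analysis.

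Two other rules bear on the point. SAP 10.0 states: "All efficacy analyses will be conducted using observed data". Protocol section 8 states: "Participants who discontinue taking study medication for any reason must also be withdrawn from the study". Visits after Day 1 begin at Week 2 (Protocol 5.1, SAP 4.0). The primary comparison is PASI 75 at Week 16, each dose against placebo, which "will be analyzed using a Chi-Square test" (SAP 10.1).

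**The concern.** Membership of the efficacy set is decided after randomisation, by whether a PASI was scored once treatment had begun. Treatment can affect that. The protocol expects some drug-related stops (section 8.1 and Table 8-1), and section 5.5 reports transaminase elevations at one earlier dose level but not at another, so early loss could differ between arms.

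A participant who leaves before any PASI is scored is in neither the numerator nor the denominator of any responder rate. This group differs from mITT members who were scored at least once but lack a Week 16 value. If the plan were improved only by counting missing Week 16 values as non-response within mITT, the second group would be restored and the first would not. The comparison would then still not be of the groups as randomised.

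**Working it through.** **Inputs.** From Protocol 10.1 and SAP 14.0: 50 randomised per arm, 20% dropout (so 40 evaluable), placebo response 6%, difference 27 points (so 33% on active), two-sided 5%, 90% power. The number leaving before a first PASI is not given. A range of k = 1 to 5 of 50 is assumed.

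**1. The plan's own figure.** The unpooled formula gives n = (1.960 + 1.282)² × (0.06 × 0.94 + 0.33 × 0.67) / 0.27² = 40 per arm, and 40 / 0.8 = 50. Exact enumeration of the uncorrected chi-square test at 40 per arm gives 90.4% power. The stated sample size reproduces and is not in dispute.

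**2. Effect under the plan as written.** Anyone with a Week 16 PASI has a score after baseline and is therefore in mITT. Anyone without a Week 16 PASI is outside an observed-data Week 16 test. The tested set is the same whether the population is called mITT or all randomised. At the planning values the dose-arm rate is 13.2 / 40 = 33%, where 13.2 = 0.33 × 40, for every value of k.

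**3. Effect if missing Week 16 scores became non-response inside mITT (not the current plan).** The expected number of responders stays at 13.2 and the denominator becomes 50 − k.

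- All randomised: 13.2 / 50 = 26.4%
- k = 1: 13.2 / 49 = 26.9%
- k = 3: 13.2 / 47 = 28.1%
- k = 5: 13.2 / 45 = 29.3%

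The overstatement is 0.5 to 2.9 points.

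**4. Direction.** On placebo, 0.06 × 40 = 2.4 responders, so 2.4 / 50 = 4.8%. The all-randomised difference is 26.4 − 4.8 = 21.6 points.

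- Five excluded from the dose arm only: 29.3 − 4.8 = 24.5
- Five excluded from each arm: 27 × 40 / 45 = 24.0
- One excluded from each arm: 27 × 40 / 49 = 22.0
- Five excluded from placebo only: 26.4 − 2.4 / 45 = 26.4 − 5.3 = 21.1

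Equal loss scales both rates by the same factor. Loss on placebo alone moves the difference against the drug.

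**5. Error rate, on the same hypothetical basis.** The true all-randomised rates are set equal and 5 of 50 are excluded from the dose arm only, so the test compares 45 with 50 (exact enumeration).

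- Both rates 26.4%: two-sided rejection 6.05%, about 6.1%, against 5.06% with nobody excluded. In the direction favouring the drug it is 4.9% against 2.5%.
- Both rates 4.8%: 3.6%
- Both rates 6%: 4.3%

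With one exclusion at 26.4% the two-sided figure is 5.2%.

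**6. Cost of the replacement.** With all 50 per arm analysed and every dropout a non-responder (26.4% v 4.8%), exact power is 89.6%. The pooled normal approximation puts power lower in both settings: 85.6% for this analysis and 87.6% for 40 observed per arm. By either method the loss is about one to two points.

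**The case against.** The strongest objection is that the population rule changes nothing on its own. Step 2 bears this out: replacing mITT with all randomised and leaving the observed-data sentence alone gives the identical Week 16 result. A reader might infer that the planned primary result is already inflated by the mITT rule. The documents do not support that, because the rates and rejection figures in steps 3 to 5 assume non-responder counting that the SAP does not contain. What remains is that correcting the observed-data rule alone would leave a gap.

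A reader might also infer that everyone who stops early is removed. That is not established. Participants return about two weeks after stopping (Protocol 5.1), an early-termination visit exists (Protocol 9.5), and Appendix 6 keeps liver-stop participants in the study for follow-up, although section 8 calls for withdrawal. A PASI at any such visit would satisfy the mITT definition. The schedule of activities is not shown, so whether one is scored there cannot be checked. Stops prompted by Week 2 blood results would also usually follow a Week 2 PASI, if one is scheduled.

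Nor are those removed necessarily treatment failures in a clinical sense. Some may be undosed, lost to follow-up or withdrawing consent. The Amendment 2 rationale treats the safety and mITT sets as much alike, which suggests that few exclusions were expected. Protocol 10.3.1 would report population counts and withdrawal reasons by arm, so exclusions would be visible. These points limit the size of the problem. They do not justify a post-randomisation entry condition with no all-randomised analysis beside it.

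**Conclusion.** The point holds in a limited form. The efficacy set depends on an event that treatment can influence, and no all-randomised analysis is planned. The rule has no separate effect on the Week 16 test under observed data, and gains one when missing scores are counted as non-response.

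Its size rests on an unstated and probably small number of participants. For 1 to 5 of 50 excluded from one dose arm, the illustrative overstatement is 0.5 to 2.9 points on a rate of 26.4%. The bias favours active drug only if early loss is concentrated in the active arms.

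A general claim of type 1 error inflation is not supported. The 6.1% figure needs five exclusions in one arm, none on placebo, and a placebo rate of 26.4% where the plan assumes 6%. With the same five exclusions at placebo-like rates, rejection is 3.6% to 4.3%, below nominal. The change is worth making because it is cheap, but the plan does not fail without it.

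**What to change.** Change two rules together, in SAP 6.1, SAP 10.0 and Protocol Table 10-1:

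- Base the primary and secondary responder analyses on all randomised participants (or all randomised and dosed), by assigned arm.
- Replace the observed-data sentence for these endpoints with a rule that a participant with no Week 16 score counts as a non-responder, including anyone with no score after baseline.
- Keep the present mITT observed-data analysis as a sensitivity analysis.

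This takes one definition, one sentence and one table row, and no new data. Response rates will be somewhat lower, and exact power is 89.6% against the stated 90% if all planned dropouts are non-responders. Changing only the population would leave the Week 16 test as it is, and changing only the missing-data rule would leave out those never scored.
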